8.3.4 Electrocardiogram (ECGs)

The ECG parameters include: ventricular rate (beats per minute), PR interval (msec), QRS interval (msec), QT interval (msec), and QTc interval (msec).

The number and percentage of patients having notable ECG interval values and newly occurring qualitative ECG abnormalities will be summarized by treatment group.

The following notable ECG interval values for each parameter will be presented as by-subject listing. Number and percentage of subjects with at least one occurrence of the below notable ECG changes will be summarized.

QT and QTc:

- (1) New >450 msec
- (2) New >480 msec
- (3) New >500 msec
- (4) Increase from baseline >30 msec
- (5) Increase from baseline >60 msec

Shift tables will also be presented for the categories of QT results (<=450, >450-480, >480-500, >500) with counts and percentages of subjects, for shift (change) from baseline.

PR:

(1) An increase >25% from baseline and PR >200 msec at any post-baseline assessment **ORS**:

(1) An increase >25% from baseline and QRS >110 msec at any post-baseline assessment

Ventricular rate:

- (1) A decrease >25% from baseline and HR <50 bpm at any post-baseline assessment
- (2) An increase >25% from baseline and HR >100 bpm at any post-baseline assessment In addition, individual subject changes will be identified through shift tables. Shift tables will be

presented for the investigator ECG interpretation (i.e., Normal, Abnormal (not clinically significant) and Abnormal (clinically significant)) with counts and percentages of subjects, for shift (change) from baseline.

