SPONSOR INFORMATION

Sponsor Office: CytoDyn, Inc.

[name]

[contact]-Work [contact]-Fax www.cytodyn.com

CONTRACT RESEARCH ORGANIZATION INFORMATION

CONFIDENTIAL Page 4 of 101

PROTOCOL SYNOPSIS

Name of Sponsor/Company:		
CytoDyn, Inc.		
Name of Study Product:		
Leronlimab (PRO 140)		
Protocol Number: Indication:		
CD15 COVID-19	Coronavirus Disease 2019 (COVID-19)	

Title of Study: A Randomized, Double Blind, Placebo Controlled Study to Evaluate the Efficacy and Safety of Leronlimab in Patients Experiencing Prolonged Coronavirus Disease 2019 (COVID-19) Symptoms [Long-Haulers]

Study Center: Up to 5 centers in the United States. Centers must have the capability of implementing appropriate infection-control measures to prevent infection of study staff and others who share the clinical site space.

Planned Number of Subjects: 50 subjects Study Development Phase: Phase 2

Indication for Use: Leronlimab is indicated for treatment of adult patients with prolonged symptoms of Coronavirus disease 2019 (COVID-19).

Objective:

The purpose of this study is to assess the safety and efficacy of leronlimab (PRO 140) administered as weekly subcutaneous injection in subjects experiencing prolonged symptoms (> 12 weeks) of COVID-19.

Study Outcomes (Endpoints):

Primary Outcome (Endpoint) Measure:

Changes from baseline in daily COVID-19-related symptom severity score through Day 56.
 Note: A set of common COVID-19-related symptoms (see patient diary template) will be evaluated daily by the patient regardless of which symptoms a subject had at baseline, as new symptoms may appear following the baseline assessment.

Secondary Outcome (Endpoints) Measures:

 Duration of COVID-19 associated symptoms from start of study treatment (Day 0) based on selfassessment using daily symptom diary.

Duration is defined as number of days when any symptoms scored as

- moderate or severe at baseline are still scored as moderate or severe (i.e., not mild or absent) through Day 56, or
- mild or absent at study entry are scored as mild or worse (i.e., not absent)through Day 56.
- Number of symptom-free days of COVID-19 associated symptoms that were present at the start of study treatment (Day 0) based on self-assessment using daily symptom diary.

CONFIDENTIAL Page 5 of 101

Name of Sponsor/Company:		
CytoDyn, Inc.		
Name of Study Product:		
Leronlimab (PRO 140)		
Protocol Number: Indication:		

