7.10. Pulse Oxygen Saturation (SpO2)

CONFIDENTIAL Page 65 of 101

Pulse Oxygen Saturation (SPO2) will be measured at Screening and V2 (pre-dose and post-dose), V4, V6, V8, V10, V12, V14, V16, V17 (EOT), and V18 (Follow-Up).

Note: Post-dose values will be recorded at V4, V6, V8, V10, V12, V14, and V16.

7.11. 12-LEAD ELECTROCARDIOGRAM

A resting supine 12-lead ECG will be conducted at the Screening Visit (V1), and Visit 17 (EOT). A 12-lead ECG will be repeated during the study only if clinically indicated and at the discretion of the treating physician. The results will be evaluated by the Investigator. The following parameters will be recorded: ventricular rate (beats per minute), PR interval (msec), QRS interval (msec), QT interval (msec), and QTc interval (msec). Additionally, the Investigator will record the overall results of the ECG reading as either normal or abnormal, and as either not clinically significant or clinically significant. If abnormalities are observed, each will be recorded.

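### The SAP applies its QT limits and QT shift table to uncorrected QT and to a site-recorded QTc with no stated correction, so heart rate alone can move the counts

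*Combined protocol and SAP*

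**What the plan says.** Protocol 7.11 schedules a resting ECG at Screening and at Visit 17 (Day 56), with repeats only if clinically indicated. Each ECG yields a ventricular rate and, among other intervals, "QT interval (msec), and QTc interval (msec". On reading, it says "The results will be evaluated by the Investigator". It mentions no central reading, common equipment or correction formula. The synopsis allows "Up to 5 centers in the United States".

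SAP 8.3.4 carries the same parameters into the analysis: "The ECG parameters include: ventricular rate (beats per minute), PR interval (msec), QRS interval (msec), QT interval (msec), and QTc interval (msec". Under a joint heading for QT and QTc it counts subjects with a new value above 450, 480 or 500 msec, and then "Increase from baseline >30 msec" and "Increase from baseline >60 msec". It adds: "Shift tables will also be presented for the categories of QT results", cut at 450, 480 and 500 msec. That sentence names QT and not QTc.

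SAP 7.7, which holds the standard calculations, covers age, BMI, change from baseline and a censoring rule for deaths. It has no rule for QTc.

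**The concern.** Two things are mixed in one set of limits.

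First, uncorrected QT varies with heart rate. Counting it against fixed limits, and using it for the only categorical QT shift table, means that some flags reflect pulse and not repolarisation. This follows from the SAP text and needs no assumption about any site's equipment.

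Second, QTc is not a defined analysis variable. An analyst following the plan would tabulate whatever was entered on the case report form. If sites' machines apply different corrections, or all apply one that over-corrects at fast rates, the count depends on site and pulse.

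At stake is how far the ECG safety table can be interpreted. With about 25 subjects per arm (50 randomised 1:1) and one scheduled post-baseline ECG, one misclassified subject moves a percentage by 1/25 = 4 points.

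**Working it through.** The documents give no calculated figure to reproduce. The limits and the number of sites come from the documents. Every QT and heart-rate value below is an assumption chosen for illustration.

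**Formulas** (HR in bpm, RR = 60/HR): Bazett QT/RR^(1/2); Fridericia QT/RR^(1/3); Framingham QT + 154(1 − RR); Hodges QT + 1.75(HR − 60).

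**1. Uncorrected QT, repolarisation held constant.** With Fridericia QTc fixed at 430 msec, QT = 430 × (60/HR)^(1/3):

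- 75 bpm: 399.2 msec; 60 bpm: 430.0; 50 bpm: 456.9.
- The slower pulse alone crosses 450 by 50 bpm. From 75 to 50 bpm the QT rise is 456.9 − 399.2 = 57.7 msec, above the 30 msec limit.
- In the other direction, 60 to 75 bpm shortens QT by 30.8 msec, which can offset a real prolongation of that size.
- At 45 bpm QT is 473.3, so 75 to 45 bpm gives 74.1 msec and passes even the 60 msec limit, but only with a 40% fall in rate.

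The size depends on the assumed relation. For a corrected value of 430 at 50 bpm, the implied QT is 430 × 1.2^(1/2) = 471.0 under Bazett, 430 + 154 × 0.2 = 460.8 under Framingham, 456.9 under Fridericia and 430 + 1.75 × 10 = 447.5 under Hodges. It depends on the starting value too: 420 under Fridericia gives 446.3 at 50 bpm, which does not cross.

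**2. One ECG, different corrections (msec).**

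| ECG | Bazett | Fridericia | Framingham | Hodges |
|---|---|---|---|---|
| QT 370, 90 bpm | 453.2 | 423.5 | 421.3 | 422.5 |
| QT 350, 100 bpm | 451.8 | 415.0 | 411.6 | 420.0 |

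Only the Bazett column exceeds 450. The QT range flagged by Bazett but not by Fridericia runs from 450 × RR^(1/2) to 450 × RR^(1/3): about 390 to 409 msec at 80 bpm, 367 to 393 at 90 and 349 to 379 at 100. At 60 bpm the two agree.

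**3. Faster pulse alone, if Bazett is used.** With Fridericia QTc constant, Bazett QTc = Fridericia QTc × (HR/60)^(1/6):

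- Constant 430: Bazett reads 451.1 at 80 bpm and first exceeds 450 at 79 bpm. Constant 400: it needs 122 bpm.
- Constant 420, 65 to 100 bpm: 425.6 to 457.3, a rise of 31.7, crossing both the 450 and the 30 msec limits.
- Constant 410, 60 to 95 bpm: 410.0 to 442.6, a rise of 32.6. The reverse change gives −32.6 and could mask a true rise.
- From a 65 bpm baseline, the rise exceeds 30 msec at 100 bpm (constant 400) down to 97 bpm (constant 430).
- The largest rise tried was 34.5 msec (constant 430, 70 to 110 bpm), so the 60 msec limit was not reached.

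**4. Does the SAP's ventricular-rate flag catch these?** It requires a change above 25% together with a rate above 100 or below 50 bpm. The changes 60 to 95, 65 to 100 and 75 to 50 bpm all stop short of those cut-offs and would not be flagged.

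**The case against.** The documents are silent on the correction. They do not say that sites differ, or that any site uses Bazett, and an ECG manual or case report form guide outside these documents could fix one formula. A reader might infer from the silence that the QTc data will be inconsistent across sites; the text supports only that the plan leaves this open. If all sites used Fridericia, the fast-pulse effect on QTc would largely disappear.

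The population argument is also limited. A sensation of rapid heartbeat is one listed symptom and one of 24 diary items, but there is no heart-rate entry criterion, and the ECG is taken at rest. No resting rates are given, so the documents do not show that these subjects have fast rates on ECG.

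A reader might go further and infer that the counts could hide or create a drug signal. Allocation is randomised and double-blind, the ECG summaries are descriptive, and all values are listed, so anyone can recompute a correction afterwards. If each site keeps one method, mixing formulas does not affect within-subject change, although Bazett's dependence on rate would.

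These points stand and set the size of the problem. They do not answer the uncorrected-QT part. One could say that QT in the shift-table sentence is shorthand for QTc, but the heading just above it names both separately, so the text would need to say so. Being able to recompute from listings also does not pre-specify which correction counts.

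**Conclusion.** The point holds as a cheap improvement to the SAP. That uncorrected QT depends on heart rate, and is counted against fixed limits and used for the shift table, rests on the text alone. How often a limit is crossed for that reason depends on the assumed starting value, pulse change and QT–rate relation.

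The QTc part is conditional. If some or all sites report Bazett, the same ECG could be flagged at one site and not at another, and a faster pulse alone could cross the 450 or the 30 msec limit. It would be wrong to say that a faster pulse triggers the limits in general: the 60 msec limit was not crossed in the Bazett scenarios, and starting from 400 msec the 450 limit needs about 122 bpm.

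The consequence is mainly noise and poorly comparable counts in a descriptive safety table. A bias between arms would need heart rate to differ between them, through the drug, recovery or chance; nothing in the documents shows that it will.

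**What to change.** Before unblinding, add to SAP 7.7: QTcF = QT / (60/ventricular rate)^(1/3), computed for every ECG from the recorded QT and ventricular rate. In SAP 8.3.4, apply the 450, 480, 500, 30 and 60 msec limits to QTcF only, and build the categorical shift table on QTcF. Keep uncorrected QT and the site-recorded QTc in by-subject listings.

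Correcting QTc alone would not be enough, because the limits on uncorrected QT and the QT shift table would remain. Any single named formula would give consistency between sites; choosing Bazett would leave the fast-pulse effect shown above.

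The cost is one derived variable and a few lines of SAP text, with no new data or procedures. Some values will differ from the QTc that investigators saw locally; the listing lets a reader reconcile them.

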8.10.6.3. ECG

All ECG values will be listed. ECG measurements will also be summarized by treatment group and presented by time point.

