4. SAMPLE SIZE DETERMINATION AND RATIONALE

This is a randomized study with two treatment groups. The subjects will be randomized to the treatment groups (leronlimab or placebo) in a 1:1 ratio.

A total of 50 subjects will be randomized in this study. The sample size is based on clinical judgment. No statistical power calculation is used to establish the sample size for this exploratory study.

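### SAP 8.3.4 names only QT for the 450/480/500 msec shift table; it should name QTc and state the correction used

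*Combined protocol and SAP*

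**What the plan says.** SAP 8.3.4 treats the two intervals as separate parameters: its list of ECG measurements ends with "QT interval (msec), and QTc interval (msec". A sub-heading naming both QT and QTc then introduces five notable-value rules: new values above 450, 480 and 500 msec (the last is "3) New >500 msec"), and increases from baseline above 30 and 60 msec. These are to be listed by subject and tabulated: "Number and percentage of subjects with at least one occurrence of the below notable ECG changes will be summarized".

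The next sentence, still under that sub-heading, is the one at issue: "Shift tables will also be presented for the categories of QT results (<=450, >450-480, >480-500, >500". It reuses the three cut-points but names QT alone.

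Protocol 7.11 sets the ECG schedule: "A resting supine 12-lead ECG will be conducted at the Screening Visit (V1), and Visit 17 (EOT". Repeats are made only if clinically indicated. Ventricular rate, QT and QTc are all recorded. Protocol 8.10.6.3 adds general reporting: "All ECG values will be listed. ECG measurements will also be summarized by treatment group and presented by time point". Neither document plans a QTc shift table in any other place, and neither names a heart-rate correction.

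**The concern.** QT shortens as heart rate rises and lengthens as it falls. Fixed cut-points on uncorrected QT therefore mix a change in heart rate with a change in repolarisation. A programmer who takes the shift-table sentence at its word would tabulate QT. Some subjects whose QTc had moved across a cut-point would then show no shift, and some whose QTc had not moved would show one.

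This is the only planned display that crosses the baseline category of the interval with its category at the end of treatment, including downward moves. If it is built on QT while the threshold counts are given for QTc, two outputs from one section can disagree about the same subject. Heart rate may also vary in this population: a sensation of fast heartbeat is a diary symptom (protocol Appendix 1, item 6), and inclusion criterion 4 admits subjects with atrial fibrillation, atrial flutter or paced rhythms.

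**Working it through.** The plan states no figure on this point, so there is nothing to reproduce. The check is how far QT and QTc can part at ordinary heart rates.

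**Inputs.** The category limits of 450, 480 and 500 msec come from SAP 8.3.4. The heart rate of 100 bpm is the SAP's own cut-off for a notable fast ventricular rate: "2) An increase >25% from baseline and HR >100 bpm at any post-baseline assessment". The other heart rates are illustrative. The correction is an assumption, so two common forms are shown as a range:

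- cube root: QT = QTc × (60/HR)^(1/3)
- square root: QT = QTc × (60/HR)^(1/2)

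**QTc of 500 msec, cube root.** At 90 bpm, 500 × (60/90)^(1/3) = 437 msec. At 100 bpm, 500 × (60/100)^(1/3) = 422 msec. Both fall in the lowest category.

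**QTc of 501 msec, which belongs in the top category.**

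| Heart rate (bpm) | QT, cube root (msec) | QT, square root (msec) |
|---|---|---|
| 75 | 465 | 448 |
| 90 | 438 | 409 |
| 100 | 423 | 388 |
| 120 | 398 | 354 |

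All but one of these (465) lie in the lowest category. The rate above which a QTc of 501 msec gives a QT of 450 msec or less is 60/(450/501)^3 = 82.8 bpm (cube root) or 60/(450/501)^2 = 74.4 bpm (square root).

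**The opposite error at slow rates.** At 50 bpm a QT of 450 msec corresponds to a QTc of 450/(60/50)^(1/3) = 423.5 msec or 450/(60/50)^(1/2) = 410.8 msec. A QT just above 450 msec would leave the lowest category although QTc is well inside it.

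**A missed shift.** Take a subject at 60 bpm at screening with QTc 450 msec; at 60 bpm QT equals QTc, so QT is also 450 msec. At the end of treatment the rate is 90 bpm and QTc is 501 msec, so QT is 438 msec (cube root) or 409 msec (square root). A QT table shows the lowest category both times. The QTc rules count the same subject as newly above 450, 480 and 500 msec, and as having an increase above 30 msec (501 − 450 = 51).

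**A false shift.** Hold QTc at 451 msec while the rate falls from 75 to 50 bpm. By cube root QT goes from 419 to 479 msec, one category up. By square root it goes from 403 to 494 msec, two categories up. QTc has not changed.

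**The case against.** The best case for leaving the text alone is that the sentence stands under a sub-heading covering both intervals, directly after thresholds that apply to both, and uses the same cut-points. On that reading it is shorthand for QT and QTc. This is plausible. A reader might infer that the SAP chose QT instead of QTc, but the text shows incomplete wording, not such a decision. The two readings still give different tables, so the sentence should be settled.

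A reader might also infer that a prolonged QTc would be presented as normal, or lost from the report. Neither follows. Section 8.3.4 attaches no such label to the lowest category; there, the word normal belongs to the investigator's overall ECG interpretation, which has its own shift table. With one scheduled post-baseline ECG, the new-value counts for QTc already record upward crossings of the same three limits, and the listings show the values. A QTc shift table would mainly add the starting category and downward moves.

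The heart-rate argument has limits too. The diary item is a patient's sensation over 24 hours, whereas the ECG is taken at rest and supine. The documents give no resting heart rates, so the number of the 50 subjects who would be misplaced cannot be estimated. The QTc finding reported for the earlier single-dose intravenous study (protocol 1.4.2.4) gives no reason to expect a signal.

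**Conclusion.** The shift-table sentence is incomplete. It names QT, omits QTc and, taken literally, produces a table that misplaces subjects in both directions when heart rate is away from 60 bpm. The size of the displacement depends on the assumed correction, but its direction does not: under either form, a QTc just above 500 msec falls in the lowest QT category once the rate passes about 74 to 83 bpm.

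The consequence is small and confined to one safety table. New QTc prolongation remains visible in the counts and listings, other displays of individual change are planned, and no efficacy result or sample-size argument is touched. This is a low-priority clarification, worth making because the variable is already collected.

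**What to change.** In SAP 8.3.4, state that the 450/480/500 msec shift table is produced on QTc. A QT version may be kept beside it, or QT may be left to the listing. In the same place, name the single heart-rate correction that applies to all subjects, and use it for the QTc threshold counts as well so that the outputs agree. Make the change before unblinding.

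The cost is a sentence or two of text and the same table run on another variable, with no new data collection. If the QTc values recorded at the sites do not share one formula, they would have to be recalculated from the recorded QT and ventricular rate, which is a small amount of extra programming.

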8.3.5 Physical Examination

All abnormal physical examination finds will be listed.

8.3.6 Urine Pregnancy Test

All data from Urine Pregnancy test will be presented as a by-subject listing.

8.3.7 Pregnancy

All data from Outcome Description Form – Pregnancy and Notification form – pregnancy will be presented as a by-subject listing.

8.3.8 Leading Questions

All data from Leading Questions will be presented as a by-subject listing.

8.3.9 Covid-19 diagonsis

All data from covid 19 diagnosis will be presented as a by-subject listing.

9. APPENDIX - PLANNED TLG

9.1 Planned by-subject listings

DISPOSITION/WITHDRAWALS (LISTINGS 16.2.1.X)
ELIGIBILTY AND PROTOCOL DEVIATIONS (LISTINGS 16.2.2.X)
EXCLUDED SUBJECTS (LISTINGS 16.2.3.X)
DEMOGRAPHICS, POPULATION, AND BASELINE CHARACTERISTICS (LISTINGS 16.2.4.X)
TREATMENT ADMINISTRATION LISTINGS (LISTINGS 16.2.5.X)
EFFICACY RESPONSE DATA (LISTINGS 16.2.6.X)
ADVERSE EVENT DATA (LISTINGS 16.2.7.X)
SAFETY DATA (LISTINGS 16.2.8.X)

9.2 Planned Summary Tables

POPULATION DISPOSITION AND PROTOCOL DEVIATIONS
POPULATION DEMOGRAPHICS AND BASELINE CHARACTERISTICS
CONCOMITANT MEDICATION USAGE
EFFICACY SUMMARIES
SAFETY SUMMARIES
ADVERSE EVENT SUMMARIES
SERIOUS ADVERSE EVENTS

LABORATORY VITAL SIGNS

PE ECG

OTHER SAFETY

10. VERSION HISTORY

This is the first version of the SAP.

